4.2. SAFETY ANALYSIS SET

Bleeding other than safety-related reactions will not be investigated here. Bleeding events will be evaluated using the same analysis set as effectiveness.

4.3. OTHER ANALYSIS SET

Not applicable. All eligible patients will be used for the analysis except the pre-designated subanalysis.

Ì		
CCI		

4.5. SAMPLE SIZE CALCULATION

This study is a retrospective analysis of the structured data in the database and all eligible patients will be used for analysis.

The results of the feasibility assessment are shown below,

Table 1. The number of patients

Patient group	Number of patients
Patients diagnosed with NVAF at 80 years or an age older than 80 and data when patients are 80 or older are available.	
Treated with apixaban	76,260
Treated with warfarin	62,453

PFIZER CONFIDENTIAL

Page 9 of 51

Note that not all of these patients are eligible for this study because no inclusion and exclusion criteria were applied when the number of patients was estimated.

In the previous study (CER3)[2], incidence rate of major bleeding and stroke/SE were 2.5% for warfarin and 1.18 % for apixaban and 1.92% for warfarin and 0.98% for apixaban, respectively. Hazard ratios for major bleeding and stroke/SE were 0.58 and 0.57, respectively. In CER3 subgroup analysis on age, hazard ratios in sub-cohort of ages ≥ 80 years were 0.59 and 0.53 for major bleeding and stroke/SE, respectively. Although populations used for analysis are different (in the CER3 study, warfarin and apixaban could be started at any age, whereas in this study, the starting date for warfarin and apixaban was restricted to ages 80 years and older), difference may not be very large because the mean age of populations in CER3 is around 77 years old in both warfarin and apixaban cohorts. Sample size calculation was performed based on the CER3 results of older age subgroup analysis.

	Assumption: Values used for calculation	Calculated results
For major bleeding		
Type I error rate	0.05	
Type II error rate	0.2	
Hazard ratio	0.59	
N ratio in apixaban and warfarin cohorts	1:1	
Event rate for warfarin	2.5%/year	
Event rate for apixaban	1.18%/year	
Total events needed		113
Estimated number of patients		6,141
For Stroke/SE		
Type I error rate	0.05	
Type II error rate	0.2	
Hazard ratio	0.53	
N ratio in apixaban and warfarin cohorts	1:1	
Event rate for warfarin	1.92%/year	
Event rate for apixaban	0.98%/year	
Total events needed		78
Estimated number of patients		5,379

Table 2. Sample size calculation

Even allowing for the fact that 1) event rate may be higher because only patients whose index date is at 80 years or older (that is, high risk population for both stroke/SE and major PFIZER CONFIDENTIAL

Page 10 of 51

bleeding) and 2) not all of patients in Table 1 above are eligible for this study, the number of eligible patients could be enough for primary safety and effectiveness analyses with appropriate statistical power.

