9. RESEARCH METHODS

9.1. Study design

This is a retrospective non-intervention observational study to evaluate the difference in safety and effectiveness between apixaban and warfarin using a database provided by Medical Data Vision Co. Ltd. (MDV Co. Ltd.). Eligible patients will be extracted from the database and allocated to the pre-defined cohorts based on the actual age, age of NVAF diagnosis and types of anticoagulant therapy.

Based on the age category and anticoagulants on the index date (a date when patients initiated an anticoagulant for prevention of stroke/SE), eligible patients will be allocated to some cohorts. Patient characteristics will be balanced by an Inverse probability of treatment weighting (IPTW) method, and risk of stroke/SE (primary effectiveness endpoint) and major bleeding (primary safety endpoint) will be compared. Hazard ratios and 95% confident intervals will be calculated by using a COX proportional hazard method.

The following definitions will be used here

• Index date: the date when warfarin or apixaban was initiated

• Baseline period: the 180 days before the index date

• Cohorts:

- > Apixaban cohorts: patients who started an anticoagulant therapy with apixaban
- > Warfarin cohorts: patients who started an anticoagulant therapy with warfarin

• Observational period:

Follow-up period starts from the next day of the index date and ends depending on following outcomes which observed first.

- 1. Major bleeding when the target outcome for the analysis is major bleeding.
- 2. Composite of (ischemic or hemorrhagic) stroke and SE when the target outcome for the analysis is the composite endpoint.
- 3. Any bleeding when the target outcome for the analysis is any bleeding.
- 4. Discontinuation of the index OAC: The index treatment will be "discontinued" if the index OAC is not prescribed within 45 days after prescription refill date (calculated from the last refill date plus days of supply) of the index OAC, even though the patient has >1 medical encounter records after more than 45 days following the prescription refill date. The supposed prescription refill date is regarded as the last day of the follow-up for discontinued patients.

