7.1.2.3. Calculation of event rate

Patients who experience a clinical endpoint event after the earlier of their discontinuation of the index OAC, switching from the index OAC, withdrawal from the database, or the end of intended follow-up period will be censored. Patients who do not experience a clinical endpoint event will be censored at the earlier of their discontinuation of the index OAC, switching from the index OAC or withdrawal from the database will be censored.

Using the number of patients who experience each endpoints and the total observation period, incidence rate of each endpoint will be calculated and be presented as per 1,000 person-years.

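### Does SAP Table 2 mislead by giving 6,141 and 5,379 as patients without a follow-up length, and by crediting the age-80+ subgroup for all its inputs?

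*SAP*

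**What the plan says.** SAP 4.5 first reports CER3, the earlier Japanese claims study, as a whole: "incidence rate of major bleeding and stroke/SE were 2.5% for warfarin and 1.18 % for apixaban", with 1.92% and 0.98% for stroke/SE and overall hazard ratios of 0.58 and 0.57. For the older patients it gives hazard ratios only: "hazard ratios in sub-cohort of ages ≥ 80 years were 0.59 and 0.53 for major bleeding and stroke/SE, respectively". It then describes the basis of the calculation: "Sample size calculation was performed based on the CER3 results of older age subgroup analysis".

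Table 2 lists type I error 0.05, type II error 0.2, a 1:1 ratio, hazard ratios of 0.59 and 0.53, and the four rates above in per cent per year. The results are 113 and 78 events. The final row of each block, "Estimated number of patients", shows 6,141 and 5,379. There is no row for follow-up.

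After the table the SAP allows that the "event rate may be higher because only patients whose index date is at 80 years or older", and that not everyone in Table 1 will be eligible. It concludes that "the number of eligible patients could be enough for primary safety and effectiveness analyses with appropriate statistical power".

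On follow-up, Protocol 9.1 says: "Follow-up period starts from the next day of the index date and ends depending on following outcomes which observed first". The listed endings are the outcome, discontinuation, switching and withdrawal, with no duration. SAP 7.1.2.3 refers to "withdrawal from the database, or the end of intended follow-up period will be censored", again with no length.

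**The concern.** Table 2 is the only power calculation, and Protocol 4.8 and 9.7 both defer to the SAP for it. Two things look wrong.

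First, dividing events by an annual rate gives exposure time. Follow-up here is on-treatment and ends after a 45-day refill gap, so mean follow-up could be well under or over a year. The number of patients needed moves in inverse proportion to it. A figure labelled as patients hides that dependence, and the adequacy sentence compares patients with what is really an exposure requirement.

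Second, the source sentence suggests that every input describes patients aged 80 or older. Only the hazard ratios do. If the wrong rates had made the requirement too small, the claim of adequate power for the two primary endpoints would rest on a weak base.

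**Working it through.** **Inputs (all SAP 4.5 and Table 2 unless noted).** Alpha 0.05, taken as two-sided; power 80%; 1:1 ratio; HR 0.59 (bleeding) and 0.53 (stroke/SE); rates 2.5 and 1.18 %/year (bleeding), 1.92 and 0.98 %/year (stroke/SE). Unscreened pools: SAP Table 1, 76,260 + 62,453 = 138,713 if no patient is in both rows; Protocol 9.7, 34,157 + 33,163 = 67,320 patients with NVAF aged 80 or older.

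**Step 1: events.** Schoenfeld's formula with equal groups is D = 4(z₀.₉₇₅ + z₀.₈₀)² / (ln HR)², with (1.9600 + 0.8416)² = 7.849.

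- Bleeding: 31.396 / 0.2784 = 112.8, rounded up to 113.
- Stroke/SE: 31.396 / 0.4031 = 77.9, rounded up to 78.

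Both match Table 2. A one-sided test (89 and 62) and Freedman's formula (119 and 84) do not. The event counts depend on the hazard ratios and not on the rates.

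**Step 2: the last row.** Events divided by the mean of the two annual rates:

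- Bleeding: (2.5 + 1.18)/2 = 1.84%/year; 113/0.0184 = 6,141.3.
- Stroke/SE: (1.92 + 0.98)/2 = 1.45%/year; 78/0.0145 = 5,379.3.

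Both match the printed figures. The unit is person-years, and the same number is a patient count when mean follow-up is one year. The arithmetic is right; the one-year convention is unstated.

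**Step 3: does the missing follow-up length matter?** Patients needed = person-years / mean follow-up. The follow-up values are assumptions, since the visible text gives none.

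| Assumed mean follow-up | Bleeding | Stroke/SE |
|---|---|---|
| 0.5 year | 12,283 | 10,759 |
| 1 year | 6,142 | 5,380 |
| 2 years | 3,071 | 2,690 |

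(The 1-year row is rounded up; Table 2 rounds to the nearest whole number.)

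The largest entry against the pools: 12,283/138,713 = 8.9%; 12,283/76,260 = 16.1% if the two rows of Table 1 overlap as far as possible; 12,283/67,320 = 18.2%.

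As a check in events, suppose 10% of the 138,713 are eligible with half a year each (both assumptions). Expected events are 13,871 × 0.5 × 0.0184 = 128 for bleeding and 13,871 × 0.5 × 0.0145 = 101 for stroke/SE, above 113 and 78. If only 10% of the smaller pool (6,732) were eligible, the mean follow-up needed would be 6,141/6,732 = 0.91 year for bleeding and 5,379/6,732 = 0.80 year for stroke/SE.

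**Step 4: does the source of the rates matter?** Required exposure is D divided by the mean rate, so higher rates mean less exposure. The SAP itself expects rates at age 80 or older to be higher if anything. On that expectation the whole-study rates overstate the requirement. The documents do not give the age-80+ rates, so a calculation resting wholly on the subgroup cannot be made from them.

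**The case for a change.** The best case for acting is that the correction is almost free (a row label and a sentence or two) and that the adequacy statement cannot be checked as written. The requirement is exposure, the comparison is with patients, and the two are linked by a follow-up length that the visible text never gives. Across 0.5 to 2 years that link changes the patient count fourfold. The source sentence is also inaccurate as it stands. The later remark that rates may be higher at age 80 or older confirms this, because it would have little purpose if the rates already came from that age group.

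The observations stand: the one-year convention is unstated, and the source sentence fits the hazard ratios only. Three parts of the case do not carry. It is too strong to say that person-years are mislabelled as patients, since at one year each the label is correct, and rates quoted per year make that the natural reading. The mixing of sources is not hidden: the same paragraph ties the rates to CER3 as a whole, ties only the hazard ratios to age 80 or older, notes that the populations differ, and prints every input. And the adequacy statement can be checked, as above, by anyone willing to assume a follow-up length.

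One limit applies. SAP 4.4 and Protocol 9.4 are withheld, so the absence of a follow-up length is established for the visible text only. SAP 4.5 itself appears complete.

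**Conclusion.** No change follows. Table 2 computes correctly from its listed inputs. What is missing is a stated one-year convention, and what is loose is one sentence about sources. A statistician reading the table recovers both from the same page.

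Rewording would alter no event count, estimate, interval, test or conclusion. The study analyses all eligible patients in an existing database, with extraction scheduled for 30 June 2022 (Protocol 4.10 and 6), so 6,141 and 5,379 set no recruitment target. The precision of the results will come from the events observed, not from Table 2.

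The adequacy statement, itself worded cautiously, holds with room to spare under ordinary assumptions. At half a year of mean follow-up it needs 8.9% of the SAP's pool (no overlap between its rows) or 18.2% of the Protocol's smaller pool to be eligible. It would come into doubt only if a low eligible fraction coincided with short follow-up, for example one tenth of the smaller pool with less than about 0.91 year each. Nothing in the documents points to that combination.

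This rests on the assumed follow-up values, on pool counts taken before full eligibility screening, and on the SAP's own expectation that rates at age 80 or older are not lower than the whole-study rates.

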5. ENDPOINTS AND COVARIATES

5.1. EFFICACY/EFFECTIVENESS ENDPOINT(S)

5.1.1. Primary effectiveness endpoint and primary analyses

Primary effectiveness endpoint is incidence of a composite of Stroke/SE ("cardiogenic cerebral embolism", "cerebral infarction", hemorrhargic stroke or SE) in NVAF patients treated with warfarin or apixaban. TIA is not included in the outcome (not regarded as stroke).

- 1. Incidence of stroke/SE (per 1,000 person-year)
- Survival curves of stroke/SE-free patients (Kaplan-Meier curves) will be drawn for apixaban and warfarin cohorts. Difference in the two curves will be evaluated by a Logrank test.

Risk of stroke/SE in each cohort will be compared between balanced warfarin and balanced apixaban cohorts by using Cox proportional hazard analysis. Hazard ratio with 95% confident intervals will be calculated.

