4.6. Variables – include exposures, outcomes, and key co-variates

• Following variables will be collected in this study at the index date (see 9.1 Study design for a definition of index date).

| | • Items | definitions | roles |
|---|--------------------------|--|-------------------------|
| ٠ | Gender | Male or female | Patient characteristics |
| • | CCI | | |
| • | Timing of NVAF diagnosis | 80-89 years ≥ 90 years | Patient characteristics |
| • | | | |
| • | Medications | Chronically prescribed medicinesDetails are shown in the SAP | Patient characteristics |
| • | | | |
| | | | |
| | | | |
| • | Stroke history | Previous diagnosis of cerebral infarction, cardiovascular embolism, hemorrhagic stroke, or TIM | Patient characteristics |

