9.2. Endpoints

- Primary effectiveness endpoint: stroke/SE (a composite of ischemic stroke, hemorrhagic stroke and SE)
- Primary safety endpoing: Major bleeding (any bleeding requiring hospitalization for treatment)

- Seconary effectiveness endpoint:
 - Cardiogenic embolic stroke
 - ➢ Ischemic stroke
- Secondary safety endpoint:
 - > Intracranial hemorrhage
 - Gastrointestinal bleeding
 - Intraocular bleeding

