9.9. Data analysis

Baseline patient demographic information will be compared among cohorts to be compared by appropriate tests (e.g., t-test, Mann Whitney-U test, chi-square test) based on the distribution of the measures.

Detailed methodology for summary and statistical analyses of data collected in this study will be documented in a statistical analysis plan (SAP), which will be dated, filed, and maintained by

the sponsor. The SAP may modify the plans outlined in the protocol; any major modifications of primary endpoint definitions or their analyses would be reflected in a protocol amendment.

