2.2. STUDY OBJECTIVES

The objective of this study is to investigate safety and effectiveness of apixaban compared to warfarin in very elderly patients with NVAF.

The purposes of this study are 1) to characterize the primary and secondary prevention patients, 2) incidence rates of stroke/SE or major bleeding in each cohort and 3) is to investigate for Japanese secondary prevention patients as RWE on the effectiveness and safety of apixaban compared to warfarin in patients with NVAF.

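### As visible, the SAP has no rule separating a new stroke/SE from an earlier one coded again, and bleeding list 10.3.4 holds three codes that name past events

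*SAP*

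**What the plan says.** **Stroke/SE endpoint.** SAP 5.1.1: "Primary effectiveness endpoint is incidence of a composite of Stroke/SE". The section names the components and takes TIA out. Protocol 9.2 gives "stroke/SE (a composite of ischemic stroke, hemorrhagic stroke and SE" and nothing further. SAP 7.1.2.3 describes the rate as follows: "Using the number of patients who experience each endpoints and the total observation period". SAP 7.1.2.4 uses time to first event. None of these sections states an admission, diagnosis-date or washout condition, and SAP Appendix 1 (data derivation) is marked as not applying.

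**Time windows and cohort.** Protocol 9.1: "Baseline period: the 180 days before the index date" and "Follow-up period starts from the next day of the index date". Prior stroke is not an exclusion criterion. Baseline stroke or SE is a propensity-score covariate in SAP 7.1.2.1, and the third purpose in SAP 2.2 "is to investigate for Japanese secondary prevention patients as RWE on the effectiveness and safety of apixaban". Protocol 4.6 defines stroke history as "Previous diagnosis of cerebral infarction, cardiovascular embolism, hemorrhagic stroke, or TIM".

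**Bleeding.** SAP 5.2.1 makes hospitalization part of the definition of major bleeding; Protocol 9.2 adds that the stay is for treatment. SAP 5.2.2 (intracranial, gastrointestinal and intraocular bleeding) states no such condition. Protocol 9.1 also lists any bleeding as a target outcome. SAP 10.3.4 is headed as the procedure that defines bleeding, and its table includes I690, I691 and T905. All three recur in the bleeding-history list in 10.3.5.

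**Redactions.** SAP 4.4, Protocol 9.4 and parts of SAP 5.4 are blacked out. No redaction is visible in SAP 5.1.1.

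**The concern.** In claims data a past stroke can be entered again under an acute code at a later visit. Here the cohort includes patients with prior stroke or SE, and follow-up opens the day after index. With no written rule, such a repeat code could be taken as a first event. A code added later in the index admission could be taken the same way.

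False events would raise the rates per 1,000 person-years in both arms, and those rates are a reported result in their own right. They could also shift the HR. Weighting balances recorded stroke history over 180 days but does not remove false events. The only planned sensitivity analysis, E-values in SAP 7.2.3, addresses unmeasured confounding, not misclassified outcomes.

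The bleeding point is more direct. If the 10.3.4 table is applied as printed, a sequela of an old intracranial bleed or injury counts as a bleeding event.

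**Working it through.** **1. Code lists side by side.** 10.3.1 gives I60, I61 and I62 for hemorrhagic stroke, I63 plus eight standard disease codes for ischemic stroke, and restricted I74 codes for SE. 10.3.3 (history) repeats these, with one added I748 line for subclavian artery stenosis. The same codes can therefore mark history and, as visible, an event.

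**2. Existing partial filters.** The stroke list shows no I69 sequelae code, and codes dated on or before index fall outside follow-up. Neither filter stops I60-I63 or I74 being entered again after index.

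**3. Sequelae codes in 10.3.4.** There are three: I690 (subarachnoid hemorrhage), I691 (intracerebral hemorrhage) and T905 (intracranial injury). Steps 2 and 3 of that section screen disease names for relevance to anticoagulant side effects, not for new versus past.

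**4. The plan's own figure (SAP Table 2, stroke/SE).** Inputs are HR 0.53, rates of 1.92 and 0.98 per 100 person-years, alpha 0.05 taken as two-sided, power 0.80 and 1:1 allocation.
- Events = 4 × (1.960 + 0.842)² / ln(0.53)² = 77.9, rounded up to 78.
- Patients = 78 / ((0.0192 + 0.0098)/2) = 78 / 0.0145 = 5,379.

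Both match Table 2.

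**5. Illustration of carry-over.** The documents give no carry-over rate, so the false-event rates Fw (warfarin) and Fa (apixaban), per 100 person-years, are assumptions. The earlier study's rates may already contain some carry-over.

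Observed HR = (true HR × 1.92 + Fa) / (1.92 + Fw), with 0.53 × 1.92 = 1.0176.

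| True HR | Fw | Fa | Calculation | Observed HR |
|---|---|---|---|---|
| 0.53 | 0.10 | 0.10 | 1.1176/2.02 | 0.55 |
| 0.53 | 0.25 | 0.25 | 1.2676/2.17 | 0.58 |
| 0.53 | 0.50 | 0.50 | 1.5176/2.42 | 0.63 |
| 0.53 | 0.25 | 0.50 | 1.5176/2.17 | 0.70 |
| 0.53 | 0.50 | 0.25 | 1.2676/2.42 | 0.52 |
| 1 | 0.50 | 0.25 | 2.17/2.42 | 0.90 |
| 1 | 0.25 | 0.50 | 2.42/2.17 | 1.12 |

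In the three equal cases with true HR 0.53, the warfarin rate rises from 19.2 to 20.2, 21.7 or 24.2 per 1,000 person-years, and the apixaban rate from 10.2 to 11.2, 12.7 or 15.2.

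A wider assumption is that 10% to 30% of patients have prior stroke and 1% to 20% of those are recoded in a year, equally in both arms. That adds 0.1 to 6 false events per 100 person-years and gives an observed HR of 0.55 to 0.89.

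**6. Power.** At 0.5 false events in both arms, the method of step 4 gives 145 events. The mean rate is (2.42 + 1.5176)/2 = 1.969 per 100, so about 7,365 patients are needed. At the extreme of 6 per 100 it gives 2,146 events and 28,733 patients. Table 1 lists 76,260 + 62,453 = 138,713 patients before eligibility criteria.

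**The case against.** **Silence is not a rule.** A reader might infer that the plan counts every repeat code as an event. No passage says so: SAP 5.1.1 speaks of incidence, 10.3.1 is headed only as a list of diagnosis codes, and a rule or a no-prior-stroke analysis could sit under a redaction (SAP 4.3 mentions a pre-designated sub-analysis). This stands. The supportable statement is that no separating rule is visible.

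**Impact is assumed.** The false-event rates have no source in the documents, and equal carry-over is conservative for a superiority hypothesis. The unequal cases show what is possible; no mechanism for them is documented, and baseline stroke/SE is weighted. A reader might infer a bias in favour of apixaban or a loss of power; the documents support neither.

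**The bleeding table may not be final.** Steps 2 and 3 act on disease names, yet the table prints whole ICD categories. Whether the sequelae names survive is not shown, and hospitalization partly guards major bleeding. This limits the harm but does not remove it for outcomes without that condition.

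**Redefinition would go too far.** A reader might conclude that the primary endpoint should become inpatient-only, with at-risk time starting at discharge. That would conflict with the follow-up start in Protocol 9.1 and the time origin in SAP 7.1.2.4. It would lose real strokes, select patients after treatment start, and could still count an old stroke coded as a comorbidity in a later stay. Applied to the primary endpoint alone, it would also leave the secondary stroke endpoints on a different basis. Under Protocol 9.9, "any major modifications of primary endpoint definitions or their analyses would be reflected in a protocol amendment", and version 2.0 (10 August 2023) already falls inside the analysis window planned in Protocol 4.10 (1 July to 31 August 2023). This objection stands, so the fix leaves the primary definition alone.

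**Conclusion.** The point holds in a limited form. As visible, nothing in SAP 5.1.1 separates a new stroke/SE from an earlier one coded again, in a cohort that includes prior-stroke patients and with history codes that nearly match the diagnosis list. Stroke/SE rates could be inflated. The HR would move toward 1 under equal carry-over and in either direction under unequal carry-over. How far cannot be derived from the documents; the table above rests on assumed rates.

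The bleeding part rests on three code names and does not depend on the redactions. It bears mainly on intracranial hemorrhage and on other bleeding outcomes with no stated hospitalization condition. It does not show that the major-bleeding analysis is invalid.

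The gap is worth correcting because no planned analysis would reveal either effect and the corrections are cheap.

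**What to change.** 1. State in the SAP that 10.3.4 defines the bleeding outcomes. Delete I690, I691 and T905 from it and keep them only as bleeding history in 10.3.5. Because 10.3.4 would also feed the primary safety endpoint, record whether this counts as a major modification under Protocol 9.9.
2. Keep the primary stroke/SE definition and the follow-up start. Add to SAP 7.2.3 a sensitivity analysis of stroke/SE in patients with no stroke/SE code in the baseline period or in earlier available data, with propensity scores re-estimated and balance rechecked.
3. If admission and diagnosis-date fields are in the extract, add a second sensitivity analysis that counts stroke/SE only when the code is newly recorded in an admission beginning after the index date. Apply it alike to the primary and secondary stroke endpoints.

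If a new-event rule already exists under a redaction, citing it in SAP 5.1.1 settles the stroke part.

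**Cost.** SAP wording, three code deletions and two extra runs. Both restricted runs have fewer events. The run in item 2 cannot speak to the secondary-prevention purpose in SAP 2.2. The run in item 3 misses strokes without admission and those during the index admission, and could still count an old stroke entered in a later stay. The documents do not say whether the date fields were extracted.
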